10.3.5. Reporting of SAEs

SAE Reporting to Pfizer Safety via an Electronic Data Collection Tool

- The primary mechanism for reporting an SAE to Pfizer Safety will be the electronic data collection tool.
- If the electronic system is unavailable, then the site will use the paper SAE data collection tool (see next section) in order to report the event within 24 hours.
- The site will enter the SAE data into the electronic system as soon as the data become available.
- After the study is completed at a given site, the electronic data collection tool will be taken off-line to prevent the entry of new data or changes to existing data.
- If a site receives a report of a new SAE from a study participant or receives updated data on a previously reported SAE after the electronic data collection tool has been taken off-line, then the site can report this information on a paper SAE form (see next section) or to Pfizer Safety by telephone.

SAE Reporting to Pfizer Safety via Vaccine SAE Reporting Form

- Facsimile transmission of the Vaccine SAE Reporting Form is the preferred method to transmit this information to Pfizer Safety.
- In circumstances when the facsimile is not working, notification by telephone is acceptable with a copy of the Vaccine SAE Reporting Form sent by overnight mail or courier service.
- Initial notification via telephone does not replace the need for the investigator to complete and sign the Vaccine SAE Reporting Form pages within the designated reporting time frames.

10.4. Appendix 4: Contraceptive Guidance

10.4.1. Male Participant Reproductive Inclusion Criteria

Male participants are eligible to participate if they agree to the following requirements during the intervention period and for at least 28 days after the last dose of study intervention:

- Refrain from donating sperm.

PLUS either:

- Be abstinent from heterosexual intercourse with a female of childbearing potential as their preferred and usual lifestyle (abstinent on a long-term and persistent basis) and agree to remain abstinent.

OR

- Must agree to use a male condom when engaging in any activity that allows for passage of ejaculate to another person.
- In addition to male condom use, a highly effective method of contraception may be considered in WOCBP partners of male participants (refer to the list of highly effective methods below in [Section 10.4.4](#)).

10.4.2. Female Participant Reproductive Inclusion Criteria

A female participant is eligible to participate if she is not pregnant or breastfeeding, and at least 1 of the following conditions applies:

- Is not a WOCBP (see definitions below in Section 10.4.3).

OR

- Is a WOCBP and using an acceptable contraceptive method as described below during the intervention period (for a minimum of 28 days after the last dose of study intervention). The investigator should evaluate the effectiveness of the contraceptive method in relationship to the first dose of study intervention.

The investigator is responsible for review of medical history, menstrual history, and recent sexual activity to decrease the risk for inclusion of a woman with an early undetected pregnancy.

10.4.3. Woman of Childbearing Potential

A woman is considered fertile following menarche and until becoming postmenopausal unless permanently sterile (see below).

If fertility is unclear (eg, amenorrhea in adolescents or athletes) and a menstrual cycle cannot be confirmed before the first dose of study intervention, additional evaluation should be considered.

Women in the following categories are not considered WOCBP:

1. Premenarchal.
2. Premenopausal female with 1 of the following:
 - Documented hysterectomy;
 - Documented bilateral salpingectomy;
 - Documented bilateral oophorectomy.

For individuals with permanent infertility due to an alternate medical cause other than the above, (eg, mullerian agenesis, androgen insensitivity), investigator discretion should be applied to determining study entry.

Note: Documentation for any of the above categories can come from the site personnel's review of the participant's medical records, medical examination, or medical history interview. The method of documentation should be recorded in the participant's medical record for the study.

3. Postmenopausal female:
 - A postmenopausal state is defined as no menses for 12 months without an alternative medical cause. In addition, a
 - high FSH level in the postmenopausal range must be used to confirm a postmenopausal state in women under 60 years of age and not using hormonal contraception or HRT.
 - Female on HRT and whose menopausal status is in doubt will be required to use one of the nonestrogen hormonal highly effective contraception methods if they wish to continue their HRT during the study. Otherwise, they must discontinue HRT to allow confirmation of postmenopausal status before study enrollment.

10.4.4. Contraception Methods

Contraceptive use by men or women should be consistent with local availability/regulations regarding the use of contraceptive methods for those participating in clinical trials.

1. Implantable progestogen-only hormone contraception associated with inhibition of ovulation.
2. Intrauterine device.
3. Intrauterine hormone-releasing system.
4. Bilateral tubal occlusion.
5. Vasectomized partner:
 - Vasectomized partner is a highly effective contraceptive method provided that the partner is the sole sexual partner of the woman of childbearing potential and the absence of sperm has been confirmed. If not, an additional highly effective method of contraception should be used. The spermatogenesis cycle is approximately 90 days.
6. Combined (estrogen- and progestogen-containing) hormonal contraception associated with inhibition of ovulation:
 - Oral;
 - Intravaginal;
 - Transdermal;
 - Injectable.
7. Progestogen-only hormone contraception associated with inhibition of ovulation:
 - Oral;
 - Injectable.
8. Sexual abstinence:
 - Sexual abstinence is considered a highly effective method only if defined as refraining from heterosexual intercourse during the entire period of risk associated with the study intervention. The reliability of sexual abstinence needs to be evaluated in relation to the duration of the study and the preferred and usual lifestyle of the participant.

9. Progestogen-only oral hormonal contraception where inhibition of ovulation is not the primary mode of action.
10. Male or female condom with or without spermicide.
11. Cervical cap, diaphragm, or sponge with spermicide.
12. A combination of male condom with either cervical cap, diaphragm, or sponge with spermicide (double-barrier methods).

10.5. Appendix 5: Liver Safety: Suggested Actions and Follow-up Assessments

Potential Cases of Drug-Induced Liver Injury

Humans exposed to a drug who show no sign of liver injury (as determined by elevations in transaminases) are termed “tolerators,” while those who show transient liver injury, but adapt are termed “adaptors.” In some participants, transaminase elevations are a harbinger of a more serious potential outcome. These participants fail to adapt and therefore are “susceptible” to progressive and serious liver injury, commonly referred to as DILI. Participants who experience a transaminase elevation above $3 \times$ ULN should be monitored more frequently to determine if they are an “adaptor” or are “susceptible.”

LFTs are not required as a routine safety monitoring procedure in this study. However, should an investigator deem it necessary to assess LFTs because a participant presents with clinical signs/symptoms, such LFT results should be managed and followed as described below.

In the majority of DILI cases, elevations in AST and/or ALT precede TBili elevations ($>2 \times$ ULN) by several days or weeks. The increase in TBili typically occurs while AST/ALT is/are still elevated above $3 \times$ ULN (ie, AST/ALT and TBili values will be elevated within the same laboratory sample). In rare instances, by the time TBili elevations are detected, AST/ALT values might have decreased. This occurrence is still regarded as a potential DILI. Therefore, abnormal elevations in either AST OR ALT in addition to TBili that meet the criteria outlined below are considered potential DILI (assessed per Hy’s law criteria) cases and should always be considered important medical events, even before all other possible causes of liver injury have been excluded.

The threshold of laboratory abnormalities for a potential DILI case depends on the participant’s individual baseline values and underlying conditions. Participants who present with the following laboratory abnormalities should be evaluated further as potential DILI (Hy’s law) cases to definitively determine the etiology of the abnormal laboratory values:

- Participants with AST/ALT and TBili baseline values within the normal range who subsequently present with AST OR ALT values $>3 \times$ ULN AND a TBili value $>2 \times$ ULN with no evidence of hemolysis and an alkaline phosphatase value $<2 \times$ ULN or not available.
- For participants with baseline AST **OR** ALT **OR** TBili values above the ULN, the following threshold values are used in the definition mentioned above, as needed, depending on which values are above the ULN at baseline:
 - Preexisting AST or ALT baseline values above the normal range: AST or ALT values >2 times the baseline values AND $>3 \times$ ULN; or $>8 \times$ ULN (whichever is smaller).

- Preexisting values of TBili above the normal range: TBili level increased from baseline value by an amount of at least $1 \times \text{ULN}$ **or** if the value reaches $>3 \times \text{ULN}$ (whichever is smaller).

Rises in AST/ALT and TBili separated by more than a few weeks should be assessed individually based on clinical judgment; any case where uncertainty remains as to whether it represents a potential Hy's law case should be reviewed with the sponsor.

The participant should return to the investigator site and be evaluated as soon as possible, preferably within 48 hours from awareness of the abnormal results. This evaluation should include laboratory tests, detailed history, and physical assessment.

In addition to repeating measurements of AST and ALT and TBili for suspected cases of Hy's law, additional laboratory tests should include albumin, CK, direct and indirect bilirubin, GGT, PT/INR, total bile acids, and alkaline phosphatase. Consideration should also be given to drawing a separate tube of clotted blood and an anticoagulated tube of blood for further testing, as needed, for further contemporaneous analyses at the time of the recognized initial abnormalities to determine etiology. A detailed history, including relevant information, such as review of ethanol, acetaminophen/paracetamol (either by itself or as a coformulated product in prescription or over-the-counter medications), recreational drug, supplement (herbal) use and consumption, family history, sexual history, travel history, history of contact with a jaundiced person, surgery, blood transfusion, history of liver or allergic disease, and potential occupational exposure to chemicals, should be collected. Further testing for acute hepatitis A, B, C, D, and E infection and liver imaging (eg, biliary tract) and collection of serum samples for acetaminophen/paracetamol drug and/or protein adduct levels may be warranted.

All cases demonstrated on repeat testing as meeting the laboratory criteria of AST/ALT and TBili elevation defined above should be considered potential DILI (Hy's law) cases if no other reason for the LFT abnormalities has yet been found. **Such potential DILI (Hy's law) cases are to be reported as SAEs, irrespective of availability of all the results of the investigations performed to determine etiology of the LFT abnormalities.**

A potential DILI (Hy's law) case becomes a confirmed case only after all results of reasonable investigations have been received and have excluded an alternative etiology.

10.6. Appendix 6: Medical Device Adverse Events, Adverse Device Effects, Serious Adverse Events, and Device Deficiencies: Definition and Procedures for Recording, Evaluating, Follow-up, and Reporting

Definitions of a Medical Device Incident

The definitions and procedures detailed in this appendix are in accordance with ISO 14155.

Both the investigator and the sponsor will comply with all local medical device reporting requirements.

The detection and documentation procedures described in this protocol apply to all sponsor medical devices provided for use in the study (see [Section 6.1.2](#) for the list of sponsor medical devices).

10.6.1. Definition of AE and ADE

AE and ADE Definition

• An AE is defined as any untoward medical occurrence, unintended disease or injury, or untoward clinical signs (including abnormal laboratory finding) in study participants, users, or other persons, whether or not related to the investigational medical device. This definition includes events related to the investigational medical device or comparator for study participants, users, and other persons. This definition also includes events considered related to procedures for study participants only.• An ADE is defined as an AE related to the use of an investigational medical device. This definition includes any AEs resulting from insufficient or inadequate instructions for use, deployment, implantation, installation, or operation, or any malfunction of the investigational medical device as well as any event resulting from use error or from intentional misuse of the investigational medical device.

10.6.2. Definition of SAE, SADE, and Unanticipated Serious Adverse Device Effect

If an event is not an AE per definition above, then it cannot be an SAE even if serious conditions are met (eg, hospitalization for signs/symptoms of the disease under study, death due to progression of disease).

An SAE is an AE that:
a. Led to death.
b. Led to serious deterioration in the health of the participant, that either resulted in:

 • A life-threatening illness or injury. The term “life-threatening” in the definition of serious refers to an event in which the participant was at risk of death at the time of the event. It does not refer to an event that hypothetically might have caused death if it were more severe. • A permanent impairment of a body structure or a body function. • Inpatient or prolonged hospitalization. Planned hospitalization for a preexisting condition, or a procedure required by the protocol, without serious deterioration in health, is not considered an SAE. • Medical or surgical intervention to prevent life-threatening illness or injury or permanent impairment to a body structure or a body function.
c. Led to fetal distress, fetal death, or a congenital abnormality or birth defect.
SADE Definition

 • An SADE is defined as an ADE that has resulted in any of the consequences characteristic of an SAE.
USADE Definition

 • A USADE is a serious adverse device effect which by its nature, incidence, severity, or outcome has not been identified in the current version of the risk analysis management file.

10.6.3. Definition of Device Deficiency

Device Deficiency Definition

 • A device deficiency is an inadequacy of a medical device with respect to its identity, quality, durability, reliability, safety, or performance. Device deficiencies include malfunctions, use errors, and inadequate labeling.

10.6.4. Recording/Reporting and Follow-up of AEs and/or SAEs and Device Deficiencies

AE, SAE, and Device Deficiency Recording

- When an AE/SAE/device deficiency occurs, it is the responsibility of the investigator to review all documentation (eg, hospital progress notes, laboratory reports, and diagnostic reports) related to the event.
- The investigator, or designee, will then record all relevant AE/SAE/device deficiency information in the participant's medical records, in accordance with the investigator's normal clinical practice: AEs/SAEs on the appropriate form of the CRF, medical device deficiencies via the medical device complaint submission form.
- It is **not** acceptable for the investigator to send photocopies of the participant's medical records to Pfizer Safety in lieu of following the reporting process described in the IP manual.
- There may be instances when copies of medical records for certain cases are requested by Pfizer Safety. In this case, all participant identifiers, with the exception of the participant number, will be redacted on the copies of the medical records before submission to Pfizer Safety.
- The investigator will attempt to establish a diagnosis of the event based on signs, symptoms, and/or other clinical information. Whenever possible, the diagnosis (not the individual signs/symptoms) will be documented as the AE/SAE.
- For device deficiencies, it is very important that the investigator describes any corrective or remedial actions taken to prevent recurrence of the incident.
 - A remedial action is any action other than routine maintenance or servicing of a medical device where such action is necessary to prevent recurrence of a device deficiency. This includes any amendment to the device design to prevent recurrence.

Assessment of Intensity

The investigator will make an assessment of intensity for each AE/SAE/device deficiency reported during the study and assign it to 1 of the following categories:

- Mild: An event that is easily tolerated by the participant, causing minimal discomfort and not interfering with everyday activities.
- Moderate: An event that causes sufficient discomfort and interferes with normal everyday activities.

- Severe: An event that prevents normal everyday activities. An AE that is assessed as severe should not be confused with an SAE. Severe is a category utilized for rating the intensity of an event; and both AEs and SAEs can be assessed as severe.
- An event is defined as “serious” when it meets at least 1 of the predefined outcomes as described in the definition of an SAE, NOT when it is rated as severe.

Assessment of Causality

- The investigator is obligated to assess the relationship between study intervention and each occurrence of each AE/SAE/device deficiency.
- A “reasonable possibility” of a relationship conveys that there are facts, evidence, and/or arguments to suggest a causal relationship, rather than a relationship cannot be ruled out.
- The investigator will use clinical judgment to determine the relationship.
- Alternative causes, such as underlying disease(s), concomitant therapy, and other risk factors, as well as the temporal relationship of the event to study intervention administration will be considered and investigated.
- The investigator will also consult the IB and/or product information, for marketed products, in his/her assessment.
- For each AE/SAE/device deficiency, the investigator **must** document in the medical notes that he/she has reviewed the AE/SAE/device deficiency and has provided an assessment of causality.
- There may be situations in which an SAE has occurred and the investigator has minimal information to include in the initial report to the sponsor. However, it is very important that the investigator always make an assessment of causality for every event before the initial transmission of the SAE data to the sponsor.
- The investigator may change his/her opinion of causality in light of follow-up information and send an SAE follow-up report with the updated causality assessment.
- The causality assessment is one of the criteria used when determining regulatory reporting requirements.

Follow-up of AE/SAE/Device Deficiency

- The investigator is obligated to perform or arrange for the conduct of supplemental measurements and/or evaluations as medically indicated or as requested by the sponsor to elucidate the nature and/or causality of the AE/SAE/device deficiency as fully as possible. This may include additional laboratory tests or investigations, histopathological examinations, or consultation with other healthcare providers.
- If a participant dies during participation in the study or during a recognized follow-up period, the investigator will provide Pfizer Safety with a copy of any postmortem findings, including histopathology.
- New or updated information will be recorded in the originally completed CRF.
- The investigator will submit any updated SAE data to the sponsor within 24 hours of receipt of the information.

10.6.5. Reporting of SAEs**SAE Reporting to Pfizer Safety via an Electronic Data Collection Tool**

- The primary mechanism for reporting an SAE to Pfizer Safety will be the electronic data collection tool.
- If the electronic system is unavailable, then the site will use the paper SAE data collection tool (see next section) in order to report the event within 24 hours.
- The site will enter the SAE data into the electronic system as soon as the data become available.
- After the study is completed at a given site, the electronic data collection tool will be taken off-line to prevent the entry of new data or changes to existing data.
- If a site receives a report of a new SAE from a study participant or receives updated data on a previously reported SAE after the electronic data collection tool has been taken off-line, then the site can report this information on a paper SAE form (see next section) or to Pfizer Safety by telephone.

SAE Reporting to Pfizer Safety via Vaccine SAE Reporting Form

- Facsimile transmission of the Vaccine SAE Reporting Form is the preferred method to transmit this information to Pfizer Safety.
- In circumstances when the facsimile is not working, notification by telephone is acceptable with a copy of the Vaccine SAE Reporting Form sent by overnight mail or courier service.
- Initial notification via telephone does not replace the need for the investigator to complete and sign the Vaccine SAE Reporting Form pages within the designated reporting time frames.

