4. STUDY DESIGN

4.1. Overall Design

This is a Phase 2b, randomized, observer-blinded, multicenter trial in which approximately 300 US participants ≥ 11 to <15 years of age will be randomly assigned at a 1:1 ratio to receive MenABCWY either on a 0- and 12-month schedule (Group 1) or a 0- and 36-month schedule (Group 2) as shown in [Section 1.2](#). All participants will be naïve to any meningococcal vaccine prior to enrollment.

Participants will have blood drawn prior to Vaccination 1 and 1 month after each vaccination. Additionally, to facilitate the description of antibody persistence after 2 doses of MenABCWY, participants in Group 1 (0- and 12-month schedule) will have blood drawn at 12 and 24 months after the second dose of MenABCWY. The sponsor will be blinded to dosing schedule assignment through Month 13 (1 month after the second dose of MenABCWY in Group 1 [0- and 12-month schedule]), after which the dosing schedule assignment for all participants will be unblinded. The second dose of MenABCWY in Group 2 (0- and 36-month schedule) will be administered in an open-label manner.

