6.1.2. Medical Devices

1. In this study, medical devices being used will be the vial adaptor and PFS for MenABCWY and the PFS only for placebo.
2. Instructions for medical device use are provided in the IP manual.
3. All medical device deficiencies (including malfunction, use error, and inadequate labeling) shall be documented and reported by the unblinded personnel throughout the clinical investigation (see [Section 8.3.6](#)) and appropriately managed by the sponsor.

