6.3.2. Blinding of Site Personnel

In this observer-blinded study, the study staff dispensing, preparing, and administering the vaccine will be unblinded. All other study and site personnel, including the investigator, investigator staff, participants, and participants' parent(s)/legal guardian, will be blinded to study intervention assignments through and including Visit 5 (Vaccinations 1 and 2). In particular, the individuals who evaluate participant safety will be blinded. Because the study vaccine and placebo are different in physical appearance, the study vaccine syringes will be administered in a manner that prevents the study participants from identifying the vaccine type based on its appearance. The second dose of MenABCWY for participants in Group 2 (Vaccination 3) will be given in an open-label manner.

The responsibility of the unblinded dispenser and administrator must be assigned to an individual or individuals who will not participate in the evaluation of any study participants. Contact between the unblinded dispenser and study participants and unblinded administrator and study participants should be kept to a minimum. The remaining site personnel must not know study intervention assignments.

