8.3.9.2. Follow-up of Medical Device Deficiencies

Follow-up applies to all participants, including those who discontinue study intervention.

The unblinded site staff are responsible for ensuring that follow-up includes any supplemental investigations as indicated to elucidate the nature and/or causality of the deficiency.

New or updated information will be recorded on a follow-up form with all changes signed and dated by the unblinded site staff.

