8.3.9.4. Regulatory Reporting Requirements for Device Deficiencies

The investigator will promptly report all device deficiencies occurring with any medical device provided for use in the study in order for the sponsor to fulfill the legal responsibility to notify appropriate regulatory authorities and other entities about certain safety information relating to medical devices being used in clinical studies.

The investigator, or responsible person according to local requirements (eg, the head of the medical institution), will comply with the applicable local regulatory requirements relating to the reporting of device deficiencies to the IRB/EC.

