### 3.5.1.1. Analysis Intervals

There will be 11 analysis intervals for the AE data collected via CRF (Table 5). The analysis populations used for these intervals are described in detail in Section 4.

For Vaccination 1 (Visit 1), MenABCWY will be administered to participants in both Groups 1 and 2. For Vaccination 2 (Visit 4), MenABCWY will be administered to Group 1 participants; saline will be administered to Group 2 participants. For Vaccination 3 (Visit 9), MenABCWY will be administered to Group 2 participants.

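### The protocol gives device deficiencies both to unblinded staff and to the blinded investigator; following the investigator text for a Visit 4 vial-adaptor fault reveals Group 1

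*Protocol*

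**What the plan says.** **Blinding.** Protocol Section 6.3.2 leaves only the staff who dispense, prepare and administer the vaccine unblinded. Everyone else at the site, "including the investigator, investigator staff, participants, and participants' parent(s)/legal guardian, will be blinded to study intervention assignments through and including Visit 5". The same section singles out those who evaluate participant safety as blinded.

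**Devices.** Protocol Section 6.1.2: "medical devices being used will be the vial adaptor and PFS for MenABCWY and the PFS only for placebo".

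**Product at Visit 4.** SAP Section 3.5.1.1: "For Vaccination 2 (Visit 4), MenABCWY will be administered to Group 1 participants; saline will be administered to Group 2 participants".

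**Deficiencies, unblinded-staff text.** Section 6.1.2 has unblinded personnel document and report all deficiencies. Section 8.3.9 gives detection and documentation to unblinded site staff. Section 8.3.9.2 adds follow-up: "The unblinded site staff are responsible for ensuring that follow-up includes any supplemental investigations as indicated to elucidate the nature and/or causality of the deficiency". Under Section 8.3.9.3 it is the unblinded staff who decide that the definition is met.

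**Deficiencies, investigator text.** Section 8.3.9.4: "The investigator will promptly report all device deficiencies occurring with any medical device provided for use in the study". Section 10.6.4 makes the investigator review the documentation, grade intensity and note the review in the medical notes, and on causality says: "The investigator is obligated to assess the relationship between study intervention and each occurrence of each AE/SAE/device deficiency". Section 10.6.6 starts the 24-hour clock for an SAE-linked deficiency when the investigator determines that the definition is met.

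**The concern.** Both sets of instructions cannot be followed while the investigator stays blinded. Visit 4 to Visit 5 is the only blinded period in which one group has just received MenABCWY and the other saline, and AEs in that phase belong to the primary safety objective. The investigator assesses the intensity and relatedness of those AEs. If a device report tells that person which product was given, the assessment for that participant is no longer blind. The leak runs one way: an adaptor report can expose a Group 1 participant and never a Group 2 participant. An entry in the medical record could also reach other blinded staff at the site.

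**Working it through.** The plan states no figure on this point, so the check is mainly a comparison of texts.

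**Step 1. Who does what.**

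| Task | Unblinded staff | Investigator |
|---|---|---|
| Detect and document | 6.1.2, 8.3.9 | 10.6.4 (recording may go to a designee) |
| Decide the definition is met | 8.3.9.3 | 10.6.6 (SAE-linked) |
| Report | 6.1.2, 8.3.9.3 | 8.3.9.4 |
| Review documentation | not stated | 10.6.4 |
| Grade intensity | not stated | 10.6.4 |
| Causality | 8.3.9.2 (follow-up) | 10.6.4 |

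The two columns overlap on four of the six tasks. No passage exempts the blinded investigator from Section 10.6.4 or says that the device record is withheld until unblinding.

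**Step 2. Which text a site would reach.** Sections 6.1.2 and 8.3 both send the reader to Section 8.3.6 for device deficiencies. Section 8.3.6 covers cardiovascular and death events and is marked not applicable. Section 8.3.9.1 sends the reader to Appendix 6 for the method of documentation, and that appendix contains the investigator text. The cross-references do not reliably lead a site to the unblinded-staff rule.

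**Step 3. What an adaptor report reveals.** Let d be the adaptor deficiency rate per MenABCWY dose. Allocation is 1:1 (Protocol Section 4.1).

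- Visit 4: P(Group 1 | report) = 0.5d / (0.5d + 0.5 × 0) = 1 for any d above zero, barring misallocation.
- Visit 1: both groups receive MenABCWY, so P(Group 1 | report) = 0.5d / (0.5d + 0.5d) = 0.5. Nothing is learned.

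Both arms use a prefilled syringe at Visit 4, so naming the syringe as the faulty device does not by itself identify the group.

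**Step 4. How often.** The documents give no deficiency rate. Purely for scale, assume 0.1% to 2% per dose (the range of event rates in Protocol Table 5, which concerns AEs, not devices) and 150 Group 1 doses at Visit 4.

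- Expected reports: 150 × 0.001 = 0.15, up to 150 × 0.02 = 3.
- Chance of at least one: 1 − (1 − 0.001)^150 = 0.14, up to 1 − (1 − 0.02)^150 = 0.95.

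Within that assumption these are upper limits. They suppose that all 150 are dosed at Visit 4, that every deficiency involves the adaptor, and that every report reaches the investigator.

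**The case against.** The strongest reply is that the trial-specific text already does the right thing. Four body sections route deficiencies to unblinded staff, and Section 6.3.2 would itself tell a careful site to keep adaptor information from the investigator. On this view Appendix 6 is text that was not aligned with the body. Section 10.6.4 also allows a designee to record, sends deficiencies through a complaint form, and refers to a reporting process in the IP manual, which is not available here and may specify blinded routing. Its intensity scale describes how a participant tolerates an event and fits poorly to a fault found during preparation.

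Much of this stands. A reader might infer that the protocol simply obliges the investigator to break the blind. It does not: exposure depends on which text the site follows. The reply does not remove the conflict, however. The designee option covers recording only; review, grading and causality have no such option. Section 8.3.9.4 is body text, not appendix text.

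A second reply concerns consequence. No hypotheses are tested. The primary safety summaries count participants with events, not related or severe events. Related events are summarized separately, and severe events only may be (SAP Sections 6.6.1.1 and 6.6.1.2). Injection-site pain was 93.4% after MenABCWY in the earlier study. The documents give no saline rate, but reactions may well be a bigger clue than a rare device report. This stands as a limit on importance.

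**Conclusion.** The protocol contradicts itself on who handles device deficiencies, and one of its two instructions defeats the blind set in Section 6.3.2. If a site follows Section 10.6.4 for an adaptor deficiency at Visit 4, the investigator learns that the participant is in Group 1. That identification is certain, barring misallocation, and rests only on the device list and the Visit 4 products.

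The size is unknown and probably small. It is confined to adaptor deficiencies at Visit 4, at sites that follow the investigator text, and bears on AE assessment in a descriptive safety comparison.

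Three wider readings are not supported:

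- A definite count of unblinded participants cannot be given, since no deficiency rate is stated.
- Visit 1 reports reveal nothing, and the documents show no comparable conflict over the medication-error page in Section 8.3.10.
- The immunogenicity assays are not affected: Section 6.3.3 keeps serology laboratory staff blinded to vaccine and visit throughout.

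**What to change.** Reconcile Sections 8.3.9.4, 10.6.4 and 10.6.6 with Sections 6.1.2 and 8.3.9 to 8.3.9.3:

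- Until the planned unblinding in Section 6.3.5, unblinded site staff review, record, assess and report device deficiencies arising at Visit 4.
- Adaptor details stay in the unblinded file and out of any record that the blinded investigator sees.
- The blinded investigator continues to assess any associated AE. Section 6.3.4 remains available if safety requires the device detail.
- SAE-linked deficiencies are still reported within 24 hours. Word the trigger so that it does not depend on the blinded investigator making the device determination.
- Redirect the references to Section 8.3.6 in Sections 6.1.2 and 8.3 to Section 8.3.9.

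The cost is protocol wording and a letter to sites. Unblinded staff already exist, although grading and causality of deficiencies would be added duties for them. The downside is that the investigator sees device detail later unless Section 6.3.4 is used. If Visit 5 is already complete, the sponsor can instead check the Visit 4 device complaint forms and disclose any that reached a blinded investigator.
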